7	3/7/2020	Due to the ongoing concern in our area regarding COVID-19, we are updating sections 12 and 18 to allow for us to take precautions to ensure the safety of our participants and staff.	
8	4/7/2020	Updates for Covid-19	yes
9	7/22/2020	Updates for CR	no

FUNDING:

Indicate any funding for this proposal. This should match the Funding Sources page in Click IRB.

Response:

This study is funded by the grant “Delay Discounting as a target for self-regulation for prediabetics” funded by NIDDK RFA-RM-14-020, “Science of Behavior Change: Assay Development and Validation for Self-Regulation Targets (UH2)”.

GRANT APPLICABILITY:

Indicate whether this protocol is funded by a grant (e.g. NIH, foundation grant). For a grant with multiple aims, indicate which aims are covered by this research proposal.

NOTE: This question does not apply to studies funded by a sponsor contract.

 *Include a copy of the grant proposal with your submission.*

Response:

This study is funded by the grant “Delay Discounting as a target for self-regulation for prediabetics” funded by NIDDK RFA-RM-14-020, “Science of Behavior Change: Assay Development and Validation for Self-Regulation Targets (UH2)”. This study was submitted and approved in request to carry forward funds from the UH2, to UH3 phase of this grant; and covers all three specific aims outlined in the application for approval to keep the carryforward funds.

1.0 Study Summary

Study Title	Imagine to Remember: Improving Medication Adherence in Pre- and Type 2 Diabetes
Study Design	Three groups, nonconcurrent multiple baseline experimental design
Primary Objective	Determine if a 4-8 week intervention consisting of future-thinking improves medication adherence
Secondary Objective(s)	Determine if a 4-8 week intervention consisting of future-thinking improves different facets of memory/executive function and/or decision-making.
Research Intervention(s)/Investigational Agent(s)	The intervention being researched is called episodic future thinking (EFT), which consists of imagining specific instances of one’s future. In this study, participants will engage in EFT pertaining to medication use, guided by a research staff member in intervention sessions across a 4-8 week period.
IND/IDE #	N/A
Study Population	Adults with prediabetes or Type 2 diabetes prescribed medication, as well as those who are at risk for developing pre and type 2 diabetes (BMI \geq 30 and hyperlipidemia or hypertension)
Sample Size	20

Study Duration for individual participants	15 weeks
Study Specific Abbreviations/ Definitions	Episodic future thinking (EFT), prospective memory (PM), working memory (WM), episodic memory (EM), and delay discounting (DD).

2.0 Objectives*

2.1 Describe the purpose, specific aims, or objectives of this research.

Response:

Aim 1: To examine whether EFT improves medication adherence.

Aim 2: To test the influence of EFT on DD (Aim 2A), and PM (Aim 2B).

2.2 State the hypotheses to be tested, if applicable.

NOTE: A hypothesis is a specific, testable prediction about what you expect to happen in your study that corresponds with your above listed objectives.

Response:

Aim 1: We hypothesize that EFT will improve medication adherence.

Aim 2: We hypothesize that EFT will reduce DD and improve PM.

3.0 Scientific Endpoints*

3.1 Describe the scientific endpoint(s), the main result or occurrence under study.

NOTE: Scientific endpoints are outcomes defined before the study begins to determine whether the objectives of the study have been met and to draw conclusions from the data. Include primary and secondary endpoints. Some example endpoints are: reduction of symptoms, improvement in quality of life, or survival. Your response should not be a date.

Response:

The primary endpoint is the increase in medication adherence and improvements in memory and decision making.

4.0 Background*

4.1 Provide the scientific or scholarly background, rationale, and significance of the research based on the existing literature and how it will contribute to existing knowledge. Describe any gaps in current knowledge. Include relevant preliminary findings or prior research by the investigator.

Response:

Adherence to medications in persons with prediabetes, type 2 diabetes or related comorbidities (e.g., hypertension, hyperlipidemia) can help prevent the development/progression of type 2 diabetes. However, adherence to diabetes medications^{1,2} and medications for its comorbidities is relatively low,³ with a commonly cited reason in those with prediabetes being “forgetting”¹. The ability to recall and successfully engage in an action at an appropriate time in the future is referred to as prospective memory (PM). Accumulating research shows that poorer prospective memory is related to medication non-adherence among individuals using various types of medications;⁴ and as such, improving PM represents a potentially fruitful means of increasing medication adherence.

An important facet of behavior that may contribute to medication non-adherence is delay discounting (DD). Delay discounting refers to the extent to which an individual devalues an outcome due to its delay in time. Prior research has shown that greater DD is related to poor glycemic control, and this relationship is partially mediated by medication adherence.⁵ Previous research by our group within the experimental medicine framework⁶, which serves as the platform for the NIH Science of Behavior Change Initiative⁷, has shown that DD is related to HbA1c levels in those with prediabetes, that changes in DD over a year are associated with changes in HbA1c, and that we can manipulate DD with episodic future thinking (or the prospection of one’s self in future scenarios; EFT). These findings set the stage for our UH3 grant on using EFT to modify DD and HbA1c levels. Several laboratory studies have shown EFT is a successful approach to improving PM⁸⁻¹¹. Given that EFT also produces robust effects on DD¹²⁻¹⁴, EFT may be an especially efficacious intervention in that it has the potential to improve two different processes related to poorer medication adherence. Current research examining the effects of EFT on PM have been confined to laboratory tasks, and research is needed to assess EFT effects on medication adherence.

We propose an RCT that will assess the effects of EFT on medication adherence, general PM, and DD among those with pre- or type 2 diabetes or related comorbidities who are currently taking at least one oral medication for diabetes or related comorbidities. We will recruit participants who are relatively non-adherent to an oral medication ($\leq 80\%$ of prescribed doses taken in the past month; to accommodate over-reporting) for prediabetes or type 2 diabetes or other conditions that commonly co-occur with these conditions (e.g., hypertension, hyperlipidemia). Medication adherence will be monitored using electronic pill bottle caps (MEMS caps, which record bottle openings with date and time stamps), pill counts, and pharmacy records. Medications for glucose control as well as control of hypertension and/or hyperlipidemia will be considered as targets for measurement. Participants self-rated as non-adherent ($\leq 80\%$ prescribed doses taken), and report difficulty remembering to take one’s medication as a primary reason for non-adherence, will undergo a 6 week, 8 week, or 10 week baseline period. After the staggered baseline periods, all participants will receive EFT intervention. In total, participants will be in baseline and treatment for a total of 15 weeks.

Randomized participants will complete bi-weekly in person sessions plus phone sessions for the weeks in which they do not come to the lab, in which they learn to engage in EFT for medication adherence. Initial EFT for medication adherence will focus on taking the targeted medication on a typical day (e.g., a weekday when the participant usually works), and in subsequent sessions EFT will be used to assist participants in adapting to unusual circumstances that may interrupt adherence or have been reported as contributing to non-adherence.

At an initial baseline session, post-intervention, and follow-up, participants will complete measures of working memory, lab-based PM, and DD. Dependent measures include change in targeted medication adherence (based on MEMS data), change in non-targeted medication adherence (for participants initially reporting non-adherence to multiple medications; based on self-report and pill count measures), DD, and PM. Moderators to be tested include working. The goal of the study will be to collect pilot data to test the feasibility and initial efficacy of the approach, as well as effect sizes for a subsequent R01.

4.2 Include complete citations or references.

Response:

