used to treat pre-diabetes, diabetes, and comorbid disorders such as hyperlipidemia and hypertension) from their current pharmacy. Participants may also complete a urine drug screen to confirm non-substance abuse and female participants may complete a urine pregnancy test to ensure eligibility. If throughout the study there is reason to believe a participant has become pregnant (i.e. the participant expresses that is their belief), we will provide pregnancy testing. If the pregnancy results are positive, the participant will be informed and they will not be eligible to continue with the study. If in-lab measures of adherence and substance use indicate that the participant does not meet study criteria, the research staff may choose to end the In-Lab Screen/Initial Assessment session early and compensation will be pro-rated (see compensation section below in protocol for details).

If participants still meet eligibility criteria and have availability for sessions, they will complete the assessments described below in the *Assessment Sessions* description. Then, the research staff will give the participant a pharmaceutical medication vial and a MEMS track-cap (an electronic medication vial cap that records and time-stamps medication vial openings). The research staff will instruct the participant to transfer their medication into the study bottle and adhere the copy of the prescription label onto the study bottle. The staff member will then review appropriate use of the study bottle and MEMS cap; and schedule the participant's intervention sessions. Participants will also have their height and weight measured.

Covid-19 Alternative Procedure: If participants still meet eligibility criteria and have availability for sessions, they will complete the assessments described below in the *Assessment Sessions* description. Then, the research staff will give the participant a pharmaceutical medication vial and a MEMS track-cap (an electronic medication vial cap that records and time-stamps medication vial openings). This will be given to participants via mail. The research staff will instruct the participant to transfer their medication into the study bottle and adhere the copy of the prescription label onto the study bottle. The staff member will then review appropriate use of the study bottle and MEMS cap via Zoom or telephone; and schedule the participant's intervention sessions.

Baseline Sessions:

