Memory tasks: Different types of memory processes may be involved in the intervention effects; these include working memory, prospective memory, retrospective memory and episodic memory, which will be measured using computerized tasks or paper/pencil measures. The tasks we will use are the following:

- The “Virtual Week” (Rendell et al., 2007; Rose et al., 2010) is a measure of Prospective Memory (PM) and Retrospective Memory (RM). The task is styled as a board game, with each round (movement across the board) representing one day. Throughout a single day, participants are instructed to complete different tasks either as different events occur (e.g., when someone comes to the door), at different times of day (e.g., when it is 4:00pm), or after different durations of gameplay. The game begins with a training round, so that the participant learns what is expected through the task. While completing the training round, the participant will be provided with any necessary instructions from the study personnel to help them complete the task correctly. After the training round, all participants will complete test rounds of the “Virtual Week.”
 - Those assigned to the EFT group may be asked to visualize completing the daily tasks prior to starting each round (e.g., close their eyes and imagine everything that would be involved with calling a fictional person in the game at a certain time).

Rendell, P. G., Jensen, F., and Henry, J. D. (2007). Prospective memory in multiple sclerosis. *J. Int. Neuropsychol. Soc.* 13, 410–416. doi: 10.1007/s00213-008-1408-0

Rose, N. S., Rendell, P. G., McDaniel, M. A., Aberle, I., and Kliegel, M. (2010). Age and individual differences in prospective memory during a “Virtual Week”: the roles of working memory, vigilance, task regularity, and cue focality. *Psychol. Aging* 25, 595–605. doi: 10.1037/A0019771

- Working memory, measured as the ability to remember sequences of items (e.g., letters, numbers, symbols, or locations), with and/or without distractors present, and potentially in different orders (e.g., forwards/backwards).
- Prospective Memory Task, measured as the ability to remember to do to an extra task (e.g., clicking the mouse, certain keys on the keyboard, typing in a text box), while finding target word's in a word list

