13.0 Study Timelines*

13.1 Describe the anticipated duration needed to enroll all study subjects.

Response:

We anticipate it will take up to 6 months to recruit all participants.

13.2 Describe the duration of an individual subject's participation in the study. Include length of study visits, and overall study follow-up time.

Response:

Participants will be in the study for approximately 15 weeks, from the time of the initial online screening survey is completed, and until the final study assessment is completed. An outline of the approximate duration of each session type and corresponding study week is provided below.

Group	Session Type	Session Duration (Hours)	Study Weeks
6-Week	Online Screen	0.5	0
	Assessment (T1)	2.5	1
	Intervention Phone Calls	0.2	7 to 14
	Intervention Sessions	0.58	7 to 14
	Assessments (T2, T3)	2	6, 15
	Total Time	13.24	
8-Week	Online Screen	0.5	0
	Assessment (T1)	2.5	1
	Intervention Phone Calls	0.2	9 to 14
	Intervention Sessions	0.58	9 to 14
	Assessments (T2, T3)	2	8, 15
	Total Time	11.68	
10-Week	Online Screen	0.5	0
	Assessment (T1)	2.5	1
	Intervention Phone Calls	0.2	11 to 14
	Intervention Sessions	0.58	11 to 14
	Assessments (T2, T3)	2	6, 15
	Total Time	10.12	

13.3 *Describe the estimated duration for the investigators to complete this study (i.e. all data is collected and all analyses have been completed).*

Response:

We anticipate the study will take approximately 1 year to complete.

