19.0 Data Management and Analysis*

19.1 Describe the data analysis plan, including any statistical procedures. This section applies to both quantitative and qualitative analysis.

Response:

Pill count and MEMS data displayed as a percentage of doses taken will be displayed graphically to enable visual analysis of changes in means and trends of dependent variables across the different phases of the study.

Borckardt, J., & Nash, M. (2014). Simulation modelling analysis for small sets of single-subject data collected over time. *Neuropsychological Rehabilitation*, 24(3-4), 492–506. <https://doi.org/10.1080/09602011.2014.895390>

19.2 If applicable, provide a power analysis.

NOTE: This may not apply to certain types of studies, including chart/records reviews, survey studies, or observational studies. This question is asked to elicit whether the investigator has an adequate sample size to achieve the study objectives and justify a conclusion.

Response:

A power analysis is not applicable to this multiple baseline design. We are collecting weekly data from participants and will have enough data points to ensure we will be able to achieve the study objectives. The results of this study will be analyzed graphically as well as assessing the degree of change from baseline to treatment across the three replications. For an example of a study that utilized a multiple baseline design, see:

19.3 Describe any procedures that will be used for quality control of collected data.

Response:

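### For the Aim 2 tasks, assessment number and EFT status coincide in every baseline tier, so practice (PM) or retest drift (DD) cannot be told from an EFT effect

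*Combined protocol and SAP*

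**What the plan says.** Section 2.2 states the Aim 2 hypothesis: "We hypothesize that EFT will reduce DD and improve PM". Section 3.1 goes further and places these outcomes in the primary endpoint: "The primary endpoint is the increase in medication adherence and improvements in memory and decision making". The Study Summary lists them as secondary.

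On timing, section 4.1 names a first baseline visit, one after the intervention and one at follow-up, at which "participants will complete measures of working memory, lab-based PM, and DD". That is one occasion before EFT and two after. Table 13.2 also has three assessments, but puts T2 at week 6, 8 or 6 (6-, 8- and 10-week tiers), with EFT sessions starting at week 7, 9 or 11. There T2 precedes EFT in every tier. Section 12.1 adds that some tasks may be given only at certain sessions, for example the first and/or the last.

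On comparison groups, sections 4.1 and 5.1 describe randomization to baseline length only, with EFT for all afterwards. Section 12.1 still describes participants doing either EFT or IC activities according to group.

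On the tasks, section 12.3 gives the Virtual Week a training round, after which "all participants will complete test rounds of the" game. No alternate task versions are mentioned for PM, working memory or DD. The DD task is a series of choices between hypothetical sums.

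On analysis, section 19.1 covers graphs of pill-count and MEMS data. Section 19.2 adds "assessing the degree of change from baseline to treatment across the three replications". No contrast, model or test is given for PM or DD.

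**The concern.** Aim 2 is a causal claim, and section 4.1 says the pilot is meant to supply effect sizes for a later grant. In a multiple baseline design, causal support comes from participants starting treatment at different times while the outcome is measured throughout. That works for weekly adherence. PM and DD are measured at most three times, and the staggering does not change which of those occasions fall before or after EFT. If people do better on a memory task simply because they have done it before, the gain lands in the same place as any EFT effect. The Aim 2 conclusion and the PM effect size carried forward would then mix the two, with the PM error in the direction of benefit.

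**Working it through.** **1. How many assessments.** The totals in table 13.2 settle this. Hours = 0.5 (screen) + 2.5 (T1) + 2k (later assessments) + weeks × (0.2 + 0.58).
- 6-week tier, 8 EFT weeks: 3.0 + 4 + 8 × 0.78 = 13.24 with k = 2, as printed.
- 8-week tier, 6 EFT weeks: 3.0 + 4 + 6 × 0.78 = 11.68, as printed.
- 10-week tier, 4 EFT weeks: 3.0 + 4 + 4 × 0.78 = 10.12, as printed.

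Section 27.1 agrees: 3 × 35 + 25 + 20 = 150.

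**2. EFT status at each occasion (table 13.2).**

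| Tier | T1 | T2 | EFT starts | T3 | T1 to T2 | T2 to T3 |
|---|---|---|---|---|---|---|
| 6-week | wk 1 | wk 6 | wk 7 | wk 15 | 5 wk | 9 wk |
| 8-week | wk 1 | wk 8 | wk 9 | wk 15 | 7 wk | 7 wk |
| 10-week | wk 1 | wk 6 | wk 11 | wk 15 | 5 wk | 9 wk |

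EFT status is (no, no, yes) in every row.

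**3. Can EFT be separated from exposure?** Take a model with three tier intercepts, separate effects for the second and third exposure, and one EFT effect: 6 parameters. Under 13.2 the EFT column equals the third-exposure column. Under 4.1 timing (no, yes, yes) it equals the sum of the second- and third-exposure columns. In both cases the design has rank 5 for 6 parameters, so the EFT effect is not identified. It becomes identified (rank 5 of 5) only if practice is assumed to be linear over occasions.

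**4. Size, as an illustration.** The documents give no practice effect, correlation, SD, test or alpha. Assumed: no EFT effect, SD 1 at each occasion, correlation r, practice gain g per repeat, and a paired t-test at two-sided 5% (2.5% in the direction of improvement). The SD of a simple change is √(2(1−r)), which is √0.6 = 0.775 at r = 0.7. The noncentrality is gain/SD × √n. For g = 0.2 and n = 12, T3-T1 has gain 0.4, so 0.4/0.775 × √12 = 1.79, which gives 37%.

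| Chance of significant improvement | g = 0.1 | g = 0.2 | g = 0.3 |
|---|---|---|---|
| T3-T1, n = 12 | 13% | 37% | 69% |
| T3-T2, n = 12 | 6% | 13% | 23% |
| T3-T1, n = 10 | 11% | 31% | 59% |

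At g = 0.2 and n = 12, moving r from 0.6 to 0.8 moves T3-T1 from 29% to 52%. If the second gain is half the first (r = 0.7, n = 12), T3-T1 is 9%, 23% or 45%.

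**5. The double difference.** (T3-T2)-(T2-T1) has a 2.5% false-positive rate if practice is linear, and 1-2% if the second gain is half the first. Its variance is 6(1−r) against 2(1−r), a ratio of 3, so its standard error is √3 = 1.73 times larger. For an assumed true EFT effect of 0.5 SD (n = 12, r = 0.7), power is 53% for T3-T2 without practice and 22% for the double difference. It is about 16% if practice is 0.2 SD then 0.1 SD.

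**The case against.** A reader might infer that the plan will report ordinary learning as an EFT effect. The documents do not go that far. The sentence in 19.2 about change from baseline to treatment follows one about weekly data, so it most naturally describes adherence. No PM or DD contrast or test is stated, and the rates above belong to a test supplied here. What the documents show is that the two explanations cannot be distinguished.

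Four other stronger readings also fail.
- **DD biased towards benefit.** The DD task has no correct answers, and nothing in the documents implies that repetition lowers discounting. Drift is possible, but its direction is unknown.
- **No allowance for practice at all.** The Virtual Week training round is a partial allowance. It limits first-exposure learning on that one task, not carry-over between sessions or learning on the other PM tasks.
- **A no-EFT change is already being collected.** Table 13.2 suggests so, but 4.1 puts the later assessments after EFT, and 12.1 lets a task skip T2.
- **Everyone gets EFT, as settled fact.** That is the stated design, but the IC text in 12.1 contradicts it. No analysis in section 19 uses an IC comparison.

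There is also a fair case against making the double difference a hurdle. It triples the variance. The gaps it compares are unequal in two tiers (5 against 9 weeks). A bare rule that T3-T2 must exceed T2-T1 would be met about half the time with no EFT effect and equal practice gains.

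What stands is the confounding itself, under either timing, and the absence of any stated PM or DD analysis that addresses it.

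**Conclusion.** The concern holds in this form. In the stated design, assessment number and EFT status coincide in all three tiers, so the staggered baselines give Aim 2 no protection. A PM change is not distinguishable from practice, and a DD change is not distinguishable from retest drift. That follows from the schedule alone and needs no assumption.

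The size does need assumptions. With 0.1 to 0.3 SD practice per repeat, the illustrative false-positive rate for PM is 13% to 69% for T3-T1 and 6% to 23% for T3-T2, against 2.5%. Choosing T2 as the reference therefore removes much of the problem but not all of it. The figures do not carry over to DD.

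**What to change.** 1. **Schedule.** Reconcile 4.1, 12.1 and 13.2 so that T2 falls before EFT in every tier and each Aim 2 task is given at T1, T2 and T3. Reconcile the IC text in 12.1 with the statement that everyone receives EFT.
2. **Analysis (19.1).** Name T2 as the pre-EFT reference for PM and DD. Report T2-T1 beside T3-T2, each with an interval, as the participants' own change without EFT. Note the unequal gaps (5/7/5 against 9/7/9 weeks).
3. **Sensitivity.** Give (T3-T2)-(T2-T1) as a sensitivity estimate, not a pass/fail rule.
4. **Wording of conclusions.** Where T3-T2 is not larger than T2-T1, describe the change as not distinguishable from practice or drift.

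Cost: mostly wording, but not entirely. The T2 tasks become a fixed scheduling commitment. The double difference will look imprecise, with 1.73 times the standard error of a simple change, which is why it should not decide the Aim 2 conclusion by itself.
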